## II. SPECIFIC AIMS

This is the third study in a series of 3 studies to develop a smartphone app to support nondaily smokers in quitting smoking, as funded by the American Cancer Society grant #RSG CPPB – 130323 (project dates: 07/01/2017 – 6/30/2021). Study 1 (2017P001106) demonstrated feasibility and acceptability when smokers were onboarded in person. Study 2 (2018P002699) demonstrated feasibility and acceptability when smokers were onboarded remotely, nationwide. The present study is Study 3. It is a 3-group proof-of-concept RCT, in which we seek to test if our app (i.e., Version 3 of our developed smartphone app, called ‘Smiling instead of Smoking’ (SiS)) is superior to treatment as usual (i.e., TAU; no treatment for nondaily smokers) and superior to a control app (i.e., the National Cancer Institute’s smartphone app “QuitGuide” (QG). Specifically, our aims are to:

1. Test for differences between randomized groups on the primary outcome of this proof-of-concept RCT, as measured at end of treatment (i.e., Week 6 post-quit): Self-efficacy to remain abstinent, as measured via the Smoking Self-Efficacy Questionnaire (SEQ): two-dimensional 12-item self-report scale measuring a person’s confidence in his or her ability to abstain from smoking when facing internal stimuli [e.g. feeling depressed] and external stimuli [e.g. being with smokers]. Participants rate each item on a sliding scale from 0 [not at all confident] to 100 [extremely confident]. Two subscale scores are created by averaging items assessing internal vs. external stimuli, respectively. We hypothesize that SiS > QG > TAU.
2. Test for differences between randomized groups on secondary outcomes:
  - a. Self-reported 30-day point-prevalence abstinence 6, 12 and 24 weeks post quit. We hypothesize that SiS > QG > TAU.
  - b. Self-reported past week cigarette reduction at 2, 6, 12, and 24 weeks post quit, compared to baseline. We hypothesize that SiS > QG > TAU.
  - c. Satisfaction with smoking cessation support, as self-rated on the Client Satisfaction Questionnaire (CSQ-8) at end of treatment. We hypothesize that SiS > QG > TAU.
  - d. Time spent applying content brought up by the apps/”Clearing the Air” at end of treatment (“During this past week, how much time did you spend applying or contemplating the content of the SiS app/QG app/”Clearing the Air”?” [in minutes]). We hypothesize that SiS > QG > TAU.

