**Analytic Plan.** All successfully enrolled participants (i.e., passed the screening process, was successfully onboarded to the assigned smoking cessation materials) will be included in the outcome analyses. For hypotheses only relevant to the SiS and QG conditions (marked in Specific Aims), only participants successfully onboarded to those conditions will be included in the analyses.

1. **Primary Outcome (Aim 1).** In this proof-of-concept RCT, the primary outcome is self-efficacy to abstain from smoking, as measured by the SEQ-12. The primary endpoint is end-of-treatment, which occurs 6 weeks after the originally chosen quit day. To test for differences between randomized groups, we will fit a fixed effects repeated measures model using PROC MIXED, where observations are modeled as nested within persons. Predictors included in the model will be GROUP (i.e., SiS vs. QG vs. TAU), TIME (i.e., BL, Week 2, Week 6, Week 12 and Week 24), and the GROUP\*TIME interaction effect. A contrast statement will be used to derive the test statistic for the GROUP comparison at Week 6, our primary endpoint, given the overall longitudinal model. This contrast statement will test the null hypothesis that SiS = QG = TAU. If this null hypothesis is rejected ( $p<0.05$ ), we will conduct pair-wise follow-up tests that compare the three possible pairwise comparisons (i.e., SiS vs. QG, SiS vs. TAU, and QG vs. TAU).
2. **Secondary Outcomes (Aim 2).** The secondary outcomes in this proof-of-concept RCT are exploratory. Thus, we will not correct for multiple testing. We will fit one model per secondary outcome, using an alpha of 0.05 for all analyses.
  - 2.1. To test for differences between randomized groups for outcomes that are assessed multiple times (Aims 2a, 2b), our overall modeling approach will be the same as for Aim 1. That is, for each outcome, we will fit a fixed effects repeated measures model, where observations are modeled as nested within persons. Predictors included in the model will be GROUP, TIME, and the GROUP\*TIME interaction effect. However, for these secondary outcomes, the definitions of the TIME effect varies across these secondary outcomes, based on their assessment schedule. The distribution of the outcome variables also varies across these variables. Thus, we will implement this overall modeling approach for these variables as follows:

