- 2.2. To test for differences between randomized groups for outcomes that are only assessed at end of treatment (Aims 2c – 2l), for each outcome, we will use a fixed effects model, where GROUP is the only predictor, and score at end of treatment is the dependent variable. Histograms will be used to guide selection of the most appropriate distribution. We anticipate that we will use the normal distribution for the CSQ-8 (Aim 2c), use of strategies (Aim 2e), perceived impact (Aim 2f), the AS (Aim 2g), actual app usage (Aim 2h), self-reported app usage (Aim 2i), likeability of the app (Aim 2j), satisfaction with the app (Aim 2k), and the SUS (Aim 2l), as implemented via the PROC MIXED procedure in SAS. We anticipate that we will use the Poisson distribution for time spent applying content (Aim 2d), as implemented via the PROC GENMOD procedure in SAS. If the GROUP effect is statistically significant ( $p<0.05$ ), we will conduct pair-wise follow-up tests that compare the three possible pairwise comparisons (i.e., SiS vs. QG, SiS vs. TAU, and QG vs. TAU). These follow-up analyses will not be necessary for secondary outcomes that are only assessed for the SiS and QG conditions (i.e., Aims 2j-2l).
3. Exploratory mediational models (Aim 3): We will use mediational modeling, using the product-of-coefficients approach and a fully lagged model to test if hypothesized within-person changes (see Figure 1) occur, and if they are linked to subsequent abstinence. The independent variable will be randomized group assignment (i.e., SiS vs. TAU), and the outcome variable will be self-reported 30-day point prevalence abstinence as measured at 6-month follow-up). The mediators will be our theorized mechanisms of change, as listed in the Aim 3 (i.e., self-efficacy, emotional well-being, desire to smoke, breadth of thought-action-repertoire, processing of processing of self-relevant health information.). Baseline values on these constructs will be included in the model to control for individual differences

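### The Poisson model anticipated for weekly minutes (Aim 2d) has no stated dispersion scaling, so its 5% group test is too liberal if the variance exceeds the mean

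*Combined protocol and SAP*

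**What the plan says.** Aim 2d (Section II, Specific Aims) asks participants, about the past week, "how much time did you spend applying or contemplating the content of the SiS app/QG app" or the booklet, with the answer in minutes. The hypothesis is that SiS exceeds QG and QG exceeds TAU.

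Item 2.2 of the Analytic Plan (Section VI) covers outcomes assessed at end of treatment. The model is one "where GROUP is the only predictor, and score at end of treatment is the dependent variable". On its form: "Histograms will be used to guide selection of the most appropriate distribution". For minutes specifically: "We anticipate that we will use the Poisson distribution for time spent applying content (Aim 2d"), "as implemented via the PROC GENMOD procedure in SAS". Pairwise tests follow "If the GROUP effect is statistically significant" at p<0.05.

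On error control, item 2 says: "The secondary outcomes in this proof-of-concept RCT are exploratory". It applies no multiplicity correction and adds: "We will fit one model per secondary outcome, using an alpha of 0.05 for all analyses".

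The plan does not mention overdispersion, a scale parameter, robust standard errors or a named alternative distribution for Aim 2d.

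**The concern.** Weekly minutes are a duration, not a count of events. A Poisson model with no scale option fixes the variance at the mean. Self-reported minutes would have to be unusually uniform to satisfy that: with a mean of 30, the SD must be √30 ≈ 5.5.

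If the variance is larger, the model understates the standard errors. The group test then rejects more often than 5%, and each false rejection opens pairwise tests with the same fault. Chance differences in engagement time could be reported as SiS outperforming a comparator.

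The dependence on the time unit shows that the model does not suit the variable. Expressing the same data in hours divides the likelihood-ratio statistic by 60.

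**Working it through.** **Inputs.** Alpha is 0.05 (Analytic Plan, item 2). There are three arms, so the group test has 2 df. The number retained is 64 per arm (Section VI, Statistical Power; 75 × 0.85 = 63.75). The documents give no mean, SD or share of zeros for minutes, so these are assumed and varied.

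**Formula.** Let φ be the ratio of variance to mean. With no true difference, the unscaled likelihood-ratio statistic is approximately φ times a chi-square variable.

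- Group test: actual size = P(χ²₂ > 5.991/φ) = 0.05^(1/φ).
- Single pair: actual size = P(χ²₁ > 3.841/φ).

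**The plan's own figure.** At φ = 1 the formula returns the stated 5%; simulation gives 4.9–5.1%.

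**Larger spread.** The simulation used gamma-Poisson data, 3 × 64 participants, mean 30, equal true means and 20,000 replicates.

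| φ | SD (min) | Group test, formula | Group test, simulated | Single pair, formula | Gated: SiS above at least one comparator | Gated: SiS > QG and QG > TAU |
|---|---|---|---|---|---|---|
| 2 | 7.7 | 22.4% | 22.5% | 16.6% | 9.8% | 0.0% |
| 5 | 12.2 | 54.9% | 54.5% | 38.1% | 26.0% | 0.9% |
| 10 | 17.3 | 74.1% | 74.4% | 53.5% | 38.3% | 2.2% |

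Even φ = 1.2 gives 8.2% for the group test. With Pearson scaling, the rate of falsely finding SiS above at least one comparator is about 2%.

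**Time unit.** A likelihood-ratio statistic of 8.7 in minutes gives p = exp(−8.7/2) = 0.013. In hours it is 8.7/60 = 0.145, giving p = 0.93. The Pearson scale also shrinks by 60, so the scaled F statistic does not change.

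**Candidate remedies, actual size at a nominal 5%, 64 per arm.**

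- *Pearson-scaled F, similar spread in all arms:* 4.8–6.0% on gamma-Poisson data (φ 2 to 30). On log-normal minutes rounded to 5 with 0–60% zeros, it is 4.9–6.0% at log-SD 0.5–0.8 and 5.9–7.2% at log-SD 1.2.
- *Robust (Wald) errors, similar spread:* 5.3–11.2%.
- *Equal means but unequal spread or zeros between arms:* unscaled Poisson group test 93.7–95.7%; Pearson F 6.0–8.6% for the group and 1.7–10.4% for single pairs; robust 6.9–9.3% for the group and 6.1–9.2% for pairs. Repeat runs gave about 1–12% for Pearson pairs and 6–10% for robust pairs.
- *Negative binomial (2,000 replicates):* 5.0% on gamma-Poisson data at φ = 10, but from 0.05% to 22.8% on the log-normal shapes.

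**Aim 2b (Analytic Plan, 2.1.2).** The dependent variable is follow-up minus baseline cigarettes, so a reduction is a negative number and lies outside the Poisson range. With an assumed baseline mean of 16 per week (4 days × 4 cigarettes, Section I.3) and SD of 6, 10 or 16, between 67% and nearly 100% of Week 6 change scores were negative across 18 assumed scenarios. Adding baseline consumption as a covariate multiplied the variance of the Week 6 SiS–TAU contrast by 0.15 to 1.00, so the gain runs from large to none.

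**The case against.** - **The plan does not say unscaled.** It names a distribution and a procedure and is silent on options. That is so. But the method as written contains nothing that would hold the test at 5%, and Poisson is the only distribution named for this outcome.
- **Poisson is only anticipated, and histograms may change it.** This has weight. An SD of 17 around a mean of 30, or many zeros, would probably be noticed, so the largest rates come from the data most likely to prompt a change. The protection is weaker near a ratio of 2, where the size is already 22%. A histogram gives no dispersion estimate, and no criterion is written.
- **The size is assumed.** Correct. The mechanism is certain; the percentages are conditional.
- **The consequence is small.** Aim 2d is one of twelve secondary outcomes (2a to 2l), all declared exploratory, and the full hypothesised ordering is falsely supported in at most about 2% of replicates. This limits the importance. But exploratory status is the plan's reason for not correcting multiplicity, not for abandoning 5% per test, and false claims against a single comparator are far more frequent.
- **The unit is fixed in minutes.** True, so no analyst choice is open. The unit argument only illustrates the misfit.
- **No remedy dominates.** With unequal spread, neither Pearson scaling nor robust errors hold single pairs at 5%. Pearson scaling does better with equal spread, and either is far better than no scaling.
- **The Aim 2b covariate corrects no error.** Agreed: the change score is valid under randomisation, and the covariate only adds precision.

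**Conclusion.** The concern holds. If the variance of weekly minutes exceeds the mean, the Poisson test as written does not have its stated 5% level. At assumed ratios of 2, 5 and 10, the actual level is about 22%, 55% and 74%. These figures rest on assumed spreads, 64 per arm, and no switch of distribution after the histograms.

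The plan should be changed before analysis, but the effect is confined to one exploratory secondary outcome. The primary analysis and the sample size do not depend on it. On Aim 2b, the Poisson example cannot be applied to the variable as defined; this is minor because the anticipated model there is normal.

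**What to change.** In item 2.2, add one sentence: any Poisson model for Aim 2d will use a Pearson-estimated scale (SCALE=PEARSON in PROC GENMOD, with F tests) for both the group test and the pairwise tests. Robust errors are an acceptable second choice, somewhat liberal at this sample size. The negative binomial should not be listed as equivalent, because its level is near 5% only when the data are close to that form. The report should note that pairwise tests remain approximate if the arms differ clearly in spread.

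In item 2.1.2, keep the normal model on the change score and delete the Poisson example. Adding baseline past-week cigarettes as a covariate is worthwhile for precision.

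The cost is one model option and one sentence for Aim 2d, and one deletion and one covariate for Aim 2b. No new data are needed and neither estimand changes.

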### III. SUBJECT SELECTION

Eligibility criteria includes the following: (a) 18+ years of age, (b) smartphone ownership (Android or iPhone only), (c) current nondaily smoker, who smokes at least weekly, and no more than 25 out of the past 30 days, and (d) lifetime history of having smoked 100+ cigarettes, and (e) is willing to make a smoking quit attempt as part of this study (f) currently residing in the United States of America. We will use both grass-root efforts (e.g., PI’s Harvard Scholar website, Craigslist, quit smoking forums) and commercial advertising (e.g., Facebook).

In addition to the aforementioned recruitment methods, we will also recruit through the RPDR (Research Patient Data Registry) at Partners Healthcare. The Research Patient Data Registry (RPDR) is supported by the dedicated team of nearly a dozen developers and support personnel. RPDR is the centralized clinical data registry/warehouse directed by Research IS & Computing’s Director, [name]. PhD. The RPDR gathers data from hospital systems and stores it in one place, bringing clinical information to a researcher’s fingertips and ensuring the security of patient information. We will run bi-weekly queries for current nondaily cigarette smokers seen at Partners Healthcare primary care sites, and subsequently submit the appropriate data requests to receive the following identifiable information: MRN (medical record number), contact information (email address, phone number, and mailing address), and RODY answer (yes/no). We will only contact patients who are designated “yes” in the Epic system, for the column “okay to contact.” Under the new MGB opt-out system, this column designates “whether it is okay to contact the patient about research recruitment. This may be based on the patient’s explicit preference, system default, or an override rule. The information displays in Yes/No format.

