## **Control Condition #2: Treatment as Usual (TAU)**

Participants in the treatment as usual (TAU) condition will be asked to make a naturalistic quit attempt, using any methods they feel might help them. To time-match the onboarding experience of SiS and QG participants, study staff will use an onboarding script to lead TAU participants through the NCI booklet “Clearing the Air”, which encourages activities in the same order as implemented in the SiS behavioral challenges (i.e., reflecting on reasons to quit, informing about benefits of quitting, logging smoking and its triggers, formulating strategies for dealing with triggers). Additionally, “Clearing the Air” provides information on smoking cessation support resources, such as counseling and pharmacological approaches.

At the end of treatment, participants complete an online survey via REDCap. This is our primary study endpoint (see Specific Aims). Participants complete two more online surveys via REDCap, occurring 12 and 24 weeks post-quit, for secondary aims.

Table 1 specifies which data are collected at which time points. Please see attached for specific descriptions of each of these measures.

Table 1. Data Collection Instruments per Time Point

Type of Measure Specific Measure	Timing of Assessment				
	BL	Wk 2	Wk 6	Wk 12	Wk 24
Primary Outcome					
Smoking Self-Efficacy Questionnaire (SEQ-12)	X	X	X	X	X
Secondary outcomes					
Smoking status	X	X	X	X	X
Recent cigarette use	X	X	X	X	X
Client Satisfaction Questionnaire (CSQ-8)			X		
Time spent applying content			X	X	X
Use of smoking cessation strategies			X		
Perceived impact of SiS/QG/TAU on quitting			X		
Appreciation Scale (AS)			X		
(SiS/QG only) Actual app usage - continuously recorded	X	X	X	X	X
(SiS/QG only) Self-reported app usage: weeks -1 to 2		X			
(SiS/QG only) Self-reported app usage: weeks 3 to 6			X		
(SiS/QG only) App likeability & satisfaction			X		
(SiS/QG only) System Usability Scale (SUS)			X		
Other outcomes to be explored in mediational analyses					
Emotional well-being					
PANAS Positive And Negative Affect Schedule (PANAS)	X	X	X	X	X
Happiness single-item measures	X	X	X	X	X
Satisfaction With Life Scale (SWLS)	X	X	X	X	X
Subjective Happiness Scale (SHS)	X	X	X	X	X
Perceived Stress Scale (PSS10)	X	X	X	X	X
Desire to smoke					
Brief Questionnaire of Smoking Urges (QSU)	X	X	X	X	X
Thought action repertoire					
Modified Twenty Statement Test (mTST) - Baseline	X				

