Modified Twenty Statement Test (mTST) - Follow-up		X	X	X	X
Processing of self-relevant health information					
Attitudes Towards Smoking (ATS)	X	X	X	X	X

Decisional Balance Inventory For Smoking (DCB-short)	X	X	X	X	X
Single-item pros and cons measures	X	X	X	X	X
Commitment To Quitting Smoking Scale (CQSS)	X	X	X	X	X
Single-item motivation measure	X	X	X	X	X
Descriptors					
Demographics	X				
Mental health diagnoses	X				
Smoking history	X				
Fagerström Test for Nicotine Dependence (FTND)	X				
Previous quit attempts	X				
Recent Quit Methods Used		X	X	X	X
E-cigarette use	X	X	X	X	X
Alcohol use	X	X	X	X	X
Smartphone use	X		X		
Center of Epidemiologic Studies Depression Scale (CES-D-10)	X	X	X	X	X
Generalized Anxiety Disorder Screener (GAD-7)	X	X	X	X	X
Snaith-Hamilton Pleasure Scale (SHAPS)	X	X	X	X	X
Life Orientation Test Revised (LOT-R)	X	X	X	X	X
State Optimism Measure (SOM)	X	X	X	X	X
Brief State Optimism Measure (BSOM)	X	X	X	X	X
Generalized Self-efficacy Scale (GSES)	X				
Personality SIMP	X				
Brief COPE	X	X	X	X	X

As noted in Table 1, in addition to outcome variables, we are also collecting descriptive information to describe the participants in this study on constructs relevant to this study:

- Demographics (at baseline, includes age, gender, ethnicity, race, education level, current student status, current employment status, total family/household income, and rurality of current residence)
- Mental health diagnoses (at baseline, “Has a doctor, nurse, or counselor ever told you that you have a mental or psychological condition?” [yes, no]. If participants select “yes,” they asked to select all that apply from a list of Axis I and II psychiatric disorders, or to specify “other mental health diagnosis.”)
- Smoking history (at baseline, captures estimated number of cigarettes participant smoked in lifetime, age when participant first tried smoking (even one or two puffs), age when participant first smoked an entire cigarette, and whether participant has ever smoked daily)
- Fagerström Test for Nicotine Dependence (FTND), a 6-item questionnaire characterizing level of physiological nicotine dependence. Answer choices are assigned numerical values which can be sum-scored to obtain level of dependence [i.e., very low dependence, low dependence, medium dependence, high dependence, or very high dependence])

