on these measures. The mediator will be scale scores observed at mid-treatment, at the 2-week assessment, which marks the end of the cessation phase. We will use multiple mediation to determine the relative importance of each mechanism, and moderated multiple mediation to identify differences in mechanisms across subgroups (e.g., males vs. females, young adult vs. older adults), similarly to our approach in delineating mechanisms of behavior change in Alcoholics Anonymous.

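### Aim 3 adjusts only for baseline mediator scores, so baseline smoking frequency and nicotine dependence can bias the non-randomised mediator-to-abstinence path

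*Combined protocol and SAP*

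**What the plan says.** Section VI, Analytic Plan item 3, describes the mediation analysis as "using the product-of-coefficients approach" within a fully lagged model. The exposure is randomised group, SiS against TAU. The outcome is "self-reported 30-day point prevalence abstinence as measured at 6-month follow-up". On timing, "The mediator will be scale scores observed at mid-treatment, at the 2-week assessment".

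The one adjustment stated is "Baseline values on these constructs will be included in the model to control for individual differences". The constructs are the five listed mechanisms: self-efficacy, emotional well-being, desire to smoke, thought-action repertoire and processing of health information. Sex and age group appear only as example moderators.

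Table 1 in section V shows that "Recent cigarette use" is collected at baseline and at every follow-up, and that the Fagerström Test for Nicotine Dependence (FTND) is collected at baseline. The analytic plan uses baseline cigarettes only for the Aim 2b change score. FTND is classed as a descriptor and has no stated analytic role. Section III admits anyone who "smokes at least weekly, and no more than 25 out of the past 30 days".

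**The concern.** Randomisation makes the group-to-mediator path causal. It does nothing for the mediator-to-abstinence path, because nobody is randomised to a Week 2 score. Any baseline characteristic that shifts both the Week 2 score and later abstinence, and is not fully captured by the baseline score, biases that path.

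Baseline smoking severity is an obvious candidate. Weekly smoking is about 30/7 = 4.3 days in 30, so eligibility spans roughly 4 to 25 smoking days. Heavier or more dependent participants could plausibly gain less self-efficacy, keep more craving and be less often abstinent at 6 months. For self-efficacy this produces a false positive coefficient, and for craving a false negative one. In both cases the bias runs in the direction that the theory predicts.

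Section II gives Aim 3 a diagnostic job. If the app does not work, Aim 3 should show whether it failed to move the mechanisms or whether the mechanisms do not drive outcome. The second answer rests on the exposed path. So does the planned ranking of mechanisms by relative importance, if severity confounds some scales more than others.

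The fully lagged structure does not help. If it means adding the baseline value of the outcome, everyone smokes at least weekly at entry, so baseline 30-day abstinence is the same for all and adjusts for nothing.

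**Working it through.** **Plan's own figure.** Section VI gives 64 per group for d = 0.50. A two-sided 5% t test has power 0.801 at n = 64 (two-sided testing and an 80% target are assumed; neither is stated). Retention: 75 × 0.85 = 63.75, about 64. The figure reproduces. It concerns self-efficacy at end of treatment; no figure is given for the mediation analysis. The simulations use 64 per arm, n = 128, which assumes the same retention at 6 months.

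**Model.** Let X be group, C standardised baseline severity, M0 the baseline mediator and M2 the Week 2 mediator. All strengths are assumed:

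- M0 = −0.3·C + noise, variance 1
- M2 = 0.5·M0 + a·X − m·C + noise of variance 0.75
- log-odds of abstinence = logit(0.20) + b·M2 − y·C, with true b = 0

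The planned analysis regresses M2 on X and M0, fits a logistic model for abstinence on X, M0 and M2, and takes a × b. The alternative adds C to both.

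**Expected bias.** Given M0, C has residual variance 1 − 0.3² = 0.91. On the log-odds scale, ignoring the slight logistic attenuation, omitting C gives

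spurious b ≈ y·m·0.91 / (0.91·m² + 0.75).

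- m = 0.2, y = 0.4: 0.0728/0.7864 = 0.093
- m = 0.3, y = 0.5: 0.1365/0.8319 = 0.164
- m = 0.4, y = 0.7: 0.2548/0.8956 = 0.285

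Simulation with 400,000 subjects and a = 0.5 gave 0.095, 0.153 and 0.270 (odds ratios 1.10, 1.17 and 1.31 per unit), and a × b of 0.047, 0.076 and 0.135. With C added, b was within 0.005 of zero. If m = 0, so that severity acts on M2 only through M0, the bias vanishes.

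**Rejection rates at n = 128** (1,500 trials, a = 0.5, true b = 0):

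| m, y | b path, as planned | b path, with C | Sobel, as planned | Sobel, with C |
|---|---|---|---|---|
| 0, 0 | 4.8% | 4.9% | 1.3% | 1.3% |
| 0.2, 0.4 | 7.1% | 5.1% | 1.9% | 1.2% |
| 0.3, 0.5 | 10.6% | 5.3% | 3.8% | 2.0% |
| 0.4, 0.7 | 20.5% | 4.5% | 6.7% | 1.0% |

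Monte Carlo error at 5% is ±1.96·√(0.05·0.95/1,500) = ±1.1 points. With a = 0, the b path still rejects in up to 20.7%, but the Sobel test rejects in 0%.

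**Second set of assumptions** (20–30% abstinent, d = 0.50 on the mediator, 1,500 trials). The three strengths are the severity–M0 correlation, the residual effect on M2 in SD, and the log-odds of abstinence per SD:

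- Weak (−0.2, −0.15, −0.4): spurious b about 0.08, b-path rejection about 5–6%
- Moderate (−0.3, −0.2, −0.5): about 0.12, 7–9%
- Strong (−0.3 to −0.4, −0.3, −0.8 to −1.0): about 0.32–0.38, 19–30%

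With severity added, rejection is 3.9–6.0%. A repeat with 2,000 trials per setting gave about 6%, 7%, 20% and 24% as planned and about 5% adjusted; Sobel rejection was about 2–10% as planned and 1–2% adjusted.

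**Several mediators together.** With four equally confounded mediators and their baselines entered jointly, b-path rejection fell to 5.7%, 6.5%, 10.3% and 12.3% across four of these settings, and Sobel rejection to 1.5–3.5%.

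**The case against.** The strongest reply is that the large figures belong to a different test. The plan specifies a product of coefficients, and the works it cites for this concern standard errors and confidence intervals for indirect effects. On that test the rate clearly passes 5% only under the strongest assumptions; a separate run of four settings gave 1.1%, 2.0%, 5.5% and 8.5%. This stands. A joint-significance test would reject more often (4–19% in that run), but the plan does not name one. The b path still matters, because item 3 also asks whether changes in the mechanisms are linked to later abstinence.

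Second, the plan enters baseline values of several constructs, and baseline craving and self-efficacy are plausible proxies for severity. This also stands: joint entry shrinks the bias, as the four-mediator run shows, though it does not remove it.

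Third, the strong setting means an odds ratio of about 0.37–0.45 per SD of severity (exp(−1.0) to exp(−0.8)). Nothing in the documents supports that, and section I describes nondaily smokers as less dependent and moved more by situation than by dependence. Accepted; the strong setting is an upper bound, not an expectation.

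Fourth, other baseline measures, such as depressive symptoms, earlier quit attempts and e-cigarette use, are arguable common causes too. True, so the proposed covariates reduce confounding without eliminating it.

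A reader might infer that the planned mediation analysis has a 20–30% false-positive rate, or that it could declare mediation when the app moves nothing. The documents support neither. The first figure is for one path under strong assumed confounding with a single mediator. On the second, a false indirect effect needs a nonzero group effect on the mediator, and with a = 0 the Sobel test never rejected.

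**Conclusion.** The omission is real. Baseline mediator scores are the only named adjustment, and collected baseline measures of smoking and dependence go unused in Aim 3. The consequence is possible bias in the mediator-to-abstinence path, and so in the conclusion on whether the mechanisms affect outcome.

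Its size cannot be fixed from the documents. It rests on assumed confounder strengths, 64 per arm at 6 months, and severity acting beyond the baseline scores. Under weak confounding the harm is hardly distinguishable from nominal error; under strong confounding it is material for that path but modest for the indirect-effect test. Aim 3 is labelled exploratory and the Week 6 primary contrast does not depend on it. The point is a cheap improvement, not a flaw in the trial's main inference.

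**What to change.** In section VI, Analytic Plan item 3, name baseline smoking severity as a covariate in both the mediator and the outcome equations of every Aim 3 model: past-week cigarettes or smoking days, and FTND. If abstinence events are few, combine them into one standardised score so that only one term is added. The outcome equation is where the bias is removed; in the mediator equation the term serves precision and consistency, since group is randomised there. Add that the mediator-to-abstinence path remains observational and may carry residual confounding.

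No new data are needed. The cost is one or two extra parameters and a standard error for the mediator coefficient about 4–14% larger in simulation. At an assumed 20–30% abstinence, 128 participants give about 26 to 38 events (128 × 0.20 = 25.6; 128 × 0.30 = 38.4), which is the reason to prefer the single score. Naming the covariates before analysis also prevents choosing them after the results are seen.
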